# 12.1 General Approach

The outcome of this design is the determination of the Maximum Tolerable Dose of ketamine infusion post-cesarean delivery. As such, the final dosing of the MTD design is the primary outcome determined as patient report of tolerated dose and acceptable side effect experiences in greater than 66% of patients.

#### 12.2 Sample Size Determination

The number of subjects (minimum of 6; maximum of 12) at each dose is dictated by traditional MTD 3+3 design, balancing the risks associated with the study drug and the assessment of adverse event rates. A formal power calculation was not performed.

# 12.3 Analysis of Primary Endpoint

Maximum Tolerated (Ketamine) Dose (MTD): The MTD will be defined as the dose at which fewer than 33% of patients experience intolerable effects.

Tolerability (dichotomous Yes/No)

- Tolerability (YES) will be defined as: lack of serious adverse events (serious adverse event defined as: severe unresolved hemodynamic effect: systolic blood pressure <80 or >160, heart rate <40 or >120).
- *Lack of Tolerability* will be defined as presence of any serious adverse event (i.e., severe unresolved hemodynamic effect: systolic blood pressure <80 or >160, heart rate <40 or >120).

For this MTD study, rates of the primary endpoint will be reported as numbers and percentages. Rates of blood pressure and heart rate events will be reported as numbers and percentages.

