# 3.4 Endpoints

# 3.4.1 Primary Endpoint

Maximum Tolerated Dose (MTD). The MTD will be defined as the dose at which fewer than 33% of patients experience a DLT defined by intolerability.

Tolerability (dichotomous Yes/No)

Tolerability (YES) will be defined as: lack of adverse events (adverse event defined as: severe unresolved hemodynamic effect: systolic blood pressure <80 or >160, heart rate <40 or >120).

Lack of Tolerability will be defined as presence of any adverse event (i.e., severe unresolved hemodynamic effect: systolic blood pressure <80 or >160, heart rate <40 or >120).

A **DLT** event is defined by complete infusion cessation due to intolerable side effect acceptability ratings by patient, OR the experience of an intolerable event as defined above. The escalation of dosing will be as noted in Figure 2 and is based on a modified Fibonacci sequence  $^{101,102}$  with smaller proportional increases in dose in the escalation scheme. Escalations occur until 2 in a cohort of 3 to 6 experiences DLT (i.e., until  $\geq$ 33% of patients experience DLT at that dose). The dose **below** this level estimates the MTD.

Participants will be classified as having had a DLT if any of the following conditions are met:

- Persisting (i.e., unresolved after 3 consecutive measurements within a 15-minute interval)
  hemodynamic side effects defined as below and despite treatments or minimizing
  infusion rates as specified.
  - Systolic blood pressure <80 or >160
  - Heart rate <40 or >120
- Complete infusion cessation due to intolerable side effect acceptability ratings by patient

Primary Outcomes will be measured at a minimum of every 4-hours from the start of the ketamine infusion (t = 0) for 24-hours (12-hours post infusion cessation). Additional assessments will be administered between the 4-hour measurements if any adverse event or side effect is noted by the patient.

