# Protocol Overview.

Patients will respond to surveys prior to and following cesarean delivery regarding their current pain and mood. Patients will begin study procedures in the third trimester of pregnancy, within approximately one week of scheduled cesarean delivery, until 12-weeks postpartum.

Preoperative weight and vital signs will be measured, and baseline inventories completed (Figure 1; refer to section 1.1). After delivery, cord clamping and declaration of clinical stability by the anesthesiologist (typically~5-15 min after delivery; ±30 minutes), a loading infusion of ketamine 0.05 mg/kg/hour will begin for the first 3-patients in the study. Vital signs and side effect symptomology will be measured 15, 30, and 60 minutes (±5 minutes) after infusion start, and at 4, 8, 10, 12, 16, and 24 hours (±30 minutes) after infusion start. Plasma samples will be collected at 1, 6, 10, and 12 hours (±30 minutes) after infusion. Any report of adverse events or side effects will trigger a blood draw for analysis and correlation of these symptoms to plasma levels of ketamine within the 12-hour infusion. All assessments have been timed to coincide with timing intervals of typical post-CD clinical care interventions. Patients dosing after the first three patients will proceed based on the MTD protocol in Figure 2; refer to section 1.1.

MTD dosing protocol.

A loading dose and maintenance infusion strategy will be used (Figure 2; in section 1.1). MTD to be tested will focus on the initial loading dose used to achieve a higher plasma concentration in a brief period. Ketamine dose will not exceed sub-anesthetic ranges (≤0.2mg/kg/hr). The maintenance rate of 0.05mg/kg/hr is based on our preliminary data suggesting tolerability, and on data suggesting that this rate might yield adequate plasma concentrations necessary for the treatment of depression. The first set of 3 patients will receive a loading infusion of ketamine 0.05 mg/kg/hr for the first data. The decision to escalate the loading infusion dose, enter 3 more at the same level, or stop, will not occur until 3 patients complete the 0.05 mg/kg/hr protocol. A **DLT** event is defined in section 3.4.1.

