If RASS -2 or below, OR Respiratory Rate is < 8	Hold infusion for 10 minutes - symptom recheck every 10 min until resolution	If no resolution within 1 hour:  D/C infusion based on investigator discretion and monitor subject for safety as described in Section 7.4 and 7.5	↓ dose by 50% (e.g., 0.05mg/kg/hr reduced to 0.025 mg/kg/hr) and continue infusion.	If no resolution within 1 hour:  D/C infusion based on investigator discretion and monitor subject for safety as described in Section 7.4 and 7.5	↓ dose by 50% (e.g., 0.025mg/kg/hr reduced to 0.013 mg/kg/hr) and continue infusion.	D/C infusion and monitor subject for safety as described in Section 7.4 and 7.5 Event qualifies as DLT
Dizziness, lightheadedness, bad dreams, persistent itchiness, hallucinations, nausea, vomiting, or other side effects rated by patient as Not Acceptable	Hold infusion for 10 minutes - symptom recheck every 10 min until resolution Supportive care medications in 9.1	If no resolution within 1 hour:  D/C infusion based on investigator discretion and monitor subject for safety as described in Section 7.4 and 7.5	↓ dose by 50% (e.g., 0.05mg/kg/hr reduced to 0.025 mg/kg/hr) and continue infusion.	If no resolution within 1 hour:  D/C infusion based on investigator discretion and monitor subject for safety as described in Section 7.4 and 7.5	↓ dose by 50%     (e.g.,     0.025mg/kg/hr     reduced to 0.013     mg/kg/hr) and     continue     infusion.	D/C infusion and monitor subject for safety as described in Section 7.4 and 7.5 Event qualifies as DLT
Nausea or Vomiting	Rescue medications as indicated in 6.6  Re-evaluate for symptom resolution 10 min after rescue medication  Hold infusion for 10 minutes - symptom recheck every 10 min until resolution	If no resolution within 1 hour:  D/C infusion based on investigator discretion and monitor subject for safety as described in Section 7.4 and 7.5	dose by 50%  (e.g., 0.05mg/kg/hr  reduced to 0.025  mg/kg/hr) and  continue  infusion.	If no resolution within 1 hour:  D/C infusion based on investigator discretion and monitor subject for safety as described in Section 7.4 and 7.5	dose by 50%  (e.g., 0.025mg/kg/hr  reduced to 0.013  mg/kg/hr) and  continue  infusion.	D/C infusion and monitor subject for safety as described in Section 7.4 and 7.5 Event qualifies as DLT

Figure 3. Dose adjustments based on patient-reported acceptability

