# 12 Statistical Analysis

By virtue of its design, the maximum tolerated dose (MTD) 3+3 design encompasses a minimum number of 6 and maximum number of 12 patients enrolled in this trial. The results identify the drug dose at which ≥33% of patients experience dose limiting toxicity, which we have defined by unacceptable side effects or adverse events. The number of subjects at each dose is dictated by traditional MTD 3+3 design, balancing the risks associated with the study drug and the assessment of adverse event rates. A formal power calculation was not performed.

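### Section 12.3 judges the primary endpoint on hemodynamic events alone, while the DLT definition in 3.4.1 also counts patient-driven infusion cessation; and 3.4.1 omits a sedation/respiratory event that Table 1 calls a DLT

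*Combined protocol and SAP*

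**What the plan says.** Section 12.3, the only section devoted to analysing the primary endpoint, defines the MTD as the dose at which fewer than 33% of patients have intolerable effects. It then says that lack of tolerability "will be defined as presence of any serious adverse event (i.e., severe unresolved hemodynamic effect: systolic blood pressure <80 or >160", or heart rate below 40 or above 120. It does not mention DLTs, infusion cessation or acceptability ratings.

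Section 3.4.1 defines the MTD by DLTs. Its list of DLT conditions has two items: persisting hemodynamic effects at the same cut-offs, and "complete infusion cessation due to intolerable side effect acceptability ratings by patient". The stopping rule is "Escalations occur until 2 in a cohort of 3 to 6 experiences DLT", and the dose below estimates the MTD. The dosing text in Section 4 says that a DLT "event is defined in section 3.4.1".

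The rest of Section 12 is also wider than 12.3. Its opening describes dose limiting toxicity as something "which we have defined by unacceptable side effects or adverse events", and 12.1 describes the primary outcome as "determined as patient report of tolerated dose and acceptable side effect experiences in greater than 66% of patients".

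Table 1 in Section 6.3 has a row that begins "If RASS -2 or below, OR Respiratory Rate is < 8" and ends, if the event does not resolve, with "Event qualifies as DLT". No item in the 3.4.1 list matches it.

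**The concern.** The trial would escalate under one definition and report its primary result under a narrower one. Every event that 12.3 counts is also counted by 3.4.1, but not the reverse, so on the same patients 12.3 can only give the same or a higher MTD. The protocol's rationale is that earlier trials did not ask patients whether side effects were acceptable. Under 12.3 that information drops out of the primary result.

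The Table 1 mismatch affects conduct as well as reporting. The sedation/respiratory event is measured by staff, and neither sedation nor respiratory depression is among the patient-rated side effects in 3.4.2. A discontinuation for it is therefore neither a hemodynamic DLT nor a patient-driven cessation. Escalation run from the 3.4.1 list could raise the dose after events that the protocol elsewhere calls dose limiting.

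With cohorts of 3 to 6 and a planned maximum of 12 patients, one reclassified patient can move the MTD by a level.

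**Working it through.** **Inputs from the documents.** The stop rule is 2 DLTs in 3 to 6 patients (3.4.1). The reporting threshold is fewer than 33% (12.3), or more than 66% tolerating (12.1). The plan gives no DLT rates and no power calculation, so there is no stated figure to reproduce. The nearest figure is 1/8 = 12.5% in Section 6.3, but that is a rate reduction, not a cessation, in people the protocol calls unrepresentative.

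**Which events count where.**

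| Event | 12.3 | 3.4.1 list | Table 1 |
|---|---|---|---|
| Unresolved SBP or HR event | yes | yes | yes |
| Cessation for patient-rated side effects | no | yes | yes |
| Unresolved RASS -2 or below, or RR below 8 | no | no | yes |

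**Worked counts.**
- One hemodynamic event and one patient-driven cessation in six: 3.4.1 gives 2/6 = 33.3% (stop; MTD is the dose below). 12.3 gives 1/6 = 16.7% (tolerated).
- Two patient-driven cessations in three: 3.4.1 gives 2/3 = 67%. 12.3 gives 0/3 = 0%.
- One patient-driven cessation and one unresolved RASS/respiratory event in six: Table 1 gives 2/6 (stop). The 3.4.1 list gives 1/6 (escalate).
- Rounding: 2/6 = 33.3% is not fewer than 33%, so it fails 3.4.1. But 4/6 = 66.7% exceeds 66%, so the same count passes 12.1.

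**Given a stop at exactly 2/6.** If a share s of DLT patients had a hemodynamic event, 12.3 counts at most 1/6 with probability 1 − s². For s = 0.25, 0.50 and 0.75 this is 0.94, 0.75 and 0.44.

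**Per dose level, 3.4.1 stops but 12.3 is below 33%.** Let h be the hemodynamic rate, c = (1 − h) × (cessation rate) the cessation-only probability, and n = 1 − h − c. Patients are independent. Discordance means at least 2 DLTs with a hemodynamic count of 0/3 or at most 1/6:

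- Stop in the first three: 3c²n + c³
- First DLT hemodynamic, then a stop: 3hn² × [(1 − h)³ − n³]
- First DLT a cessation, then a stop: 3cn² × [(1 − h)³ + 3h(1 − h)² − n³]

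Example with h = 0.05 and cessation rate 0.125: c = 0.11875 and n = 0.83125. The terms are 0.037 + 0.029 + 0.103 = 0.169.

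| Cessation rate (assumed) | h = 5% | h = 10% |
|---|---|---|
| 5% | 0.051 | 0.062 |
| 12.5% | 0.169 | 0.177 |
| 20% | 0.308 | 0.299 |
| 30% | 0.487 | 0.447 |

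With cessation rates of 1% to 3% the result is 0.008 to 0.035.

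**Per dose level, the 3.4.1 list passes but Table 1 stops.** A level passes with probability P(p) = q³ + 3pq² × q³, where q = 1 − p. With 3.4.1 DLT rate p and RASS/respiratory rate r, the gap is P(p) − P(1 − (1 − p)(1 − r)). Example: p = 0.10 and r = 0.05 give 0.906 − 0.824 = 0.082.

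| p (assumed) | r = 2% | r = 5% | r = 10% |
|---|---|---|---|
| 5% | 0.022 | 0.063 | 0.150 |
| 10% | 0.031 | 0.082 | 0.176 |
| 20% | 0.035 | 0.087 | 0.173 |

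With r of 0.5% to 1% the gap is 0.005 to 0.017.

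**The case against.** The best defence is that 12.3 is an incomplete restatement and sets up no rival procedure. Section 3.4.1 contains almost the same hemodynamic-only tolerability text and adds cessation only afterwards, through its DLT definition. The MTD comes out of the escalation, Section 4 sends that to 3.4.1, and both the Section 12 opening and 12.1 bring in side effects. Nothing tells an analyst to derive a second MTD from 12.3. On the second point, Table 1 carries its own DLT label, the version history says the table now specifies the qualifying events, and a DSMB reviews DLT data. Figure 2 is not shown and may state the rule.

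These arguments make a wrong decision less likely but do not remove the conflict. Section 12.3 gives a complete yes/no definition with no reference to 3.4.1, and the primary endpoint rates it promises would follow that definition. Section 4 refers to 3.4.1 for the DLT definition, not to Table 1, and no figure would change the conflicting text.

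Three points stand. The probabilities depend on assumed rates, and complete cessation should be rarer than rate reduction, because in Table 1 the DLT label comes only after holds and up to two halvings. The documents do not settle whether Table 1 or the 3.4.1 list should prevail. And Table 1 also labels a nausea/vomiting row a DLT without requiring an unacceptable rating, a similar loose end.

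**Conclusion.** The concern holds on both counts and needs correcting, because it touches the sole primary endpoint and the escalation decision. The inconsistency and its direction follow from the text alone. Its frequency does not: assuming hemodynamic rates of 5% to 10% and cessation rates of 5% to 30%, the two definitions disagree on 5% to 49% of dose levels, falling to about 1% to 4% if cessation is as rare as 1% to 3%. For the sedation/respiratory event the range is 2% to 18% (event rate 2% to 10%, 3.4.1 DLT rate 5% to 20%), or about 0.5% to 2% at event rates of 0.5% to 1%. All of these assume independence between event types and between patients.

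**What to change.** - Replace the tolerability definition in 12.3, and the paraphrases in the Section 12 opening and 12.1, with a cross-reference to the 3.4.1 DLT definition. Report DLT counts by component and dose.
- Add unresolved RASS -2 or below, or respiratory rate below 8, to the 3.4.1 list. This follows the version history's statement that Table 1 specifies the DLT events. If the sponsor intends otherwise, the label should come out of Table 1 with a reason.
- State the rule everywhere as counts: 0/3 or at most 1/6 passes; 2 or more DLTs stops. This removes the 33%/66% ambiguity at 2/6.
- As clarifications, say whether the separate nausea/vomiting row requires a rating of not acceptable (Figure 3, not shown, may already do so), and that discontinuation at the second or third action counts as a DLT.

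The cost is protocol wording. More events will count than under 12.3 or the present 3.4.1 list, so the reported MTD may be one level lower.

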# 12.4 Analysis of Secondary Endpoints

Side effect acceptability ratings will be reported for each side effect reported as numbers and percentages. Examination of patient pain and depression scores in the 12-weeks post cesarean delivery will be explored. The limited sample size of the MTD design precludes definitive conclusions regarding pain and depression. General linear mixed models will be used to assess trends in pain and depression over the peripartum period according to dose exposure. Paired t-tests may be used to assess changes in pain or depression scores from the preterm to postpartum 12-week assessments.

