# Side Effect Acceptability Ratings

Any reported side effects are rated by patients. Patient reported side effects (i.e., dizziness, lightheadedness, bad dreams, nausea, vomiting, itchiness, and hallucinations: all dichotomous outcomes) will be evaluated based on patient-specific reports of how "acceptable" or "unacceptable" the side effects are for continued or future use of the study medication. Patient-reported acceptability is defined based on theoretical framework of acceptability and focused on constructs of Burden ("Would experiencing side effects keep you from participating in this intervention (ketamine) again?" yes/no) and Affective Attitude ("Based on your experience with this medication, would you be willing to participate in this intervention (ketamine) again?" yes/no).

- 1. Acceptability is the absence of patient-centered unacceptable side effects. Patients with side effects who report that the side effects were "acceptable" on digital diary will be counted as having confirmed **side effect** acceptability ratings, regardless of the presence of any side effects to the ketamine dose. Patient-reported acceptability is defined as a "yes" to Affective Attitude with a "no" to Burden.
- 2. Unacceptability is any patient report of unacceptable side effects, defined as any positive response on the digital side effect diary rated unacceptable by the patient. Either a negative response to Attitude, or a positive response to Burden, will define patient unacceptability.

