#### Side Effect Acceptability Ratings.

Our existing and previously tested **digital diary** will automate alerts for questions about side effects after infusion start at 15-, 30-, 60- minutes, and every 4 hours in the first 24 hours after infusion start (Figure 1, section 1.1). The diary has been tested and used by our group in previous work; alerts coincide with RASS assessments and similar timing of clinical assessments for routine CD nursing care and monitoring (i.e., is not more burdensome or intrusive to patients than routine clinical post-CD care). The digital diary will assess side effects

(i.e., dizziness, lightheadedness, bad dreams, nausea, vomiting, itchiness, and hallucinations: all dichotomous outcomes). Any positive response to any item will trigger the subject to rate their acceptability of side effects in the following way. Patient-reported acceptability is defined based on theoretical framework of acceptability and focused on constructs of *Burden* ("Would experiencing side effects keep you from participating in this intervention (ketamine) again?" yes/no) and *Affective Attitude* ("Based on your experience with this medication, would you be willing to participate in this intervention (ketamine) again?" yes/no). Either a negative response to Attitude, or a positive response to Burden, will define patient unacceptability.

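### Section 12.4 reports acceptability for each side effect, but the rating questions name no effect, so an unacceptable rating is misattributed when co-occurring effects differ in acceptability

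*Combined protocol and SAP*

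**What the plan says.** All references are to the combined protocol and SAP.

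- **Reporting unit.** Section 12.4: "Side effect acceptability ratings will be reported for each side effect reported as numbers and percentages".
- **Items.** Sections 3.4.2 and 7 list seven effects, each answered yes or no: "dizziness, lightheadedness, bad dreams, nausea, vomiting, itchiness, and hallucinations: all dichotomous outcomes".
- **Trigger.** Section 7, Side Effect Acceptability Ratings: "Any positive response to any item will trigger the subject to rate their acceptability of side effects in the following way".
- **Burden question.** "Would experiencing side effects keep you from participating in this intervention (ketamine) again" (yes/no).
- **Affective Attitude question.** "Based on your experience with this medication, would you be willing to participate in this intervention (ketamine) again" (yes/no).
- **Classification.** "Either a negative response to Attitude, or a positive response to Burden, will define patient unacceptability". Section 3.4.2 also describes unacceptability as "defined as any positive response on the digital side effect diary rated unacceptable by the patient".
- **Repetition.** Section 7 schedules "questions about side effects after infusion start at 15-, 30-, 60- minutes, and every 4 hours in the first 24 hours", which makes nine alerts. Appendix 2 marks ten diary times, adding hour 10.

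Section 3.3.2 gives side effect acceptability as the one secondary objective. Section 3.4.2 lists it as the first of three secondary endpoints. Section 1 projects at most 12 patients with complete primary outcome data.

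**The concern.** The planned table has one row per side effect, but the rating behind it is not tied to any one effect. Burden asks about side effects collectively and Attitude asks about the medication. No rule says how a single answer is to be divided among effects reported together. Suppose a patient reports nausea, dizziness and itchiness and objects only to the nausea. The data then hold one unacceptable rating and three endorsed effects. Applying Section 12.4 literally produces three unacceptable entries where the patient meant one.

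At stake is the descriptive table for the secondary objective. Sections 2.1 and 2.2 justify the trial partly by noting that earlier work did not ask patients about acceptability, so readers will look to this table to learn which effects patients will not accept. Cross-tabulating co-occurring effects afterwards cannot show which one the patient had in mind.

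**Working it through.** The plan states no figure on this point, so there is none to reproduce. The check compares the questions with the reporting unit, then illustrates the size under stated assumptions.

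**1. Questions against reporting unit.** Section 12.4 needs a rating for each pair of patient and effect. Sections 3.4.2 and 7 supply two answers whose wording names no effect, and either answer alone can classify the patient as finding the drug unacceptable. With one endorsed effect there is only one to which the answer can be credited. With two or more that differ in acceptability, the per-effect rating cannot be identified.

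**2. Rate credited to a milder effect.** Assume the answer is unacceptable whenever any effect present is unacceptable. Let uA and uB be the true unacceptability rates of effects A and B, taken as independent, and let q be the probability that A is present given B. Then

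reported rate for B = uB + (1 − uB) × q × uA.

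If B is always acceptable (uB = 0), this is q × uA:

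| q | uA | True rate for B | Reported rate for B |
|---|---|---|---|
| 0 | any | 0% | 0% |
| 0.25 | 0.2 | 0% | 5% |
| 0.5 | 0.4 | 0% | 20% |
| 1 | 0.6 | 0% | 60% |

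The values of q and uA are assumptions; the documents give none.

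**3. The same in counts (assumed).** Six patients have nausea, and three of them find it unacceptable. Six have dizziness, and all find it acceptable. The true figure for dizziness is 0/6. If c patients have both, the number of dizziness reports wrongly credited lies between max(0, 3 − (6 − c)) and min(3, c):

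| c | Reported for dizziness |
|---|---|
| 0 | 0/6 |
| 2 | 0/6 to 2/6 |
| 4 | 1/6 to 3/6 |
| 6 | 3/6 (50%) |

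**4. How often entries hold several effects.** If the seven effects were independent with common prevalence p, the chance of two or more given at least one is P(X ≥ 2)/P(X ≥ 1) with X ~ Binomial(7, p). This is 29%, 54%, 73% and 87% for p = 10%, 20%, 30% and 40%. Both the prevalence and the independence are assumed, and correlation between effects would change these values.

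**5. Smallest shift.** Section 12.4 does not say whether the percentages are of patients or of diary entries.
- Patients, at most 12: one misattributed patient moves the effect's rate by at least 1/12 = 8.3 percentage points, and by more if only patients reporting that effect are counted.
- All scheduled entries, at most 12 × 10 = 120: one misattributed entry moves it by 1/120 = 0.8 points. A patient misattributed at all ten times moves it by 10/120 = 8.3 points.

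**The case against.** The strongest reply is that the diary's branching is not documented. It is an existing instrument that the protocol does not reproduce. The trigger sentence in Section 7, and the Section 3.4.2 phrase that attaches the rating to a positive response, could both describe one rating per endorsed item. That is fair: a reader might infer that acceptability is put only once for all effects together, and the documents do not establish this. It does not remove the problem. Repeating the printed questions unchanged for each item would still name no effect, and Attitude asks about the medication as a whole. Because a negative Attitude answer is enough to define unacceptability, repetition would still mark every endorsed effect.

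Three further limits stand.

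- A reader might conclude that per-effect rates are wrong whenever effects co-occur. They are wrong only when the co-occurring effects differ in acceptability.
- A reader might treat 8.3 points as a floor in all cases. It needs a patient-level denominator of at most 12, which Section 12.4 does not state.
- A reader might infer that the same rating also selects between rows of Table 1 in Section 6.3. The documents do not support that: the endorsed symptom determines the row, and the separate nausea or vomiting row carries no acceptability condition.

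It is also true that the secondary objective concerns acceptability of the infusion, which the printed questions can answer at patient level.

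**Conclusion.** The concern holds in a limited form. Applying the Section 12.4 reporting rule to the questions as printed misattributes unacceptability whenever an entry contains effects that differ in acceptability. If the patient's answer follows the worst effect, the bias overstates unacceptability of the milder ones.

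The consequence is confined to the descriptive per-effect table. Single-effect entries can be attributed. Overall patient-level acceptability is unaffected, and the DLT rule in Section 3.4.1 does not use per-effect rates.

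The size cannot be fixed from the documents, which give neither co-occurrence nor denominator. Under the assumptions shown, a fully acceptable effect could be reported as unacceptable in anything from 0% to 60% of its reports. This is more than missing detail, because the table bears on the only listed secondary objective and the attribution cannot be recovered once the data are collected. It should be corrected, but it does not threaten the primary result.

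**What to change.** **Preferred: amend Section 12.4 only.** Report acceptability per patient, using the worst rating, and per assessment, stating the denominator for each. Tabulate side-effect frequencies separately. Restrict any per-effect acceptability to entries with a single endorsed effect. The cost is a sentence or two and no change to the diary. The per-effect results will then rest on fewer entries.

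**Alternative: change the diary.** Ask Burden once for each endorsed effect with that effect named, ask Attitude once per entry, and base per-effect acceptability on the named Burden answer alone. Repeating Attitude per effect would not help, for the reason given above. The cost is at most one extra question per endorsed effect: with k effects, k + 1 questions instead of 2, so at most 8 when all seven are endorsed. That burden matters because Section 11.2 withdraws and replaces participants who miss 20% or more of diary responses.

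If the existing diary already names the effect, the protocol should print that wording, and Section 12.4 should state which answer feeds the per-effect table.
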